#### **5.4.3. Surgical/Rehabilitation Period**

The broadest span of time for the surgical/rehabilitation period is from the first dose of rFIXFc given for the surgery (i.e., the pre-surgery dose) up to 1 minute before the first regular prophylactic dose after the last day of postoperative care/rehabilitation. Since not all patients will have these events, specific considerations for the start and end of the surgical/rehabilitation period are as follows:

	Statistical Analysis Plan	Final v1.0
---	----------------------------------	-------------------

Start of the surgical/rehabilitation period:

- If there is more than one pre-surgical dose then the first one should be selected (a pre-surgical dose can be administered the day before the surgery).
- If there is no pre-surgical dose but there is a prophylaxis dose or dose given for “OTHER” reason prior to the surgery on the day of or the day before surgery, the last of these doses should be selected.
- If there is no pre-surgical dose or a prophylactic dose the day before surgery then select the start date/time of the surgery. If the time was not recorded then select the date and impute 00:01 for the time.

End of the surgical/rehabilitation period:

- 1 minute before the first regular prophylactic dose on or after the last date among the dates for discharge from the hospital, post-operative visit 1, post-operative visit 2, and the end of rehabilitation.
- If all of the dates mentioned above are missing, then select the first prophylactic dose after the date/time for the end of surgery. If the surgery time was not recorded then select the surgery date and impute 23:59 for the time. If the end date of the surgery is missing then select the start date of the surgery and impute 23:59 for the time.
- If the patient is not on prophylactic regimen following the surgical/rehabilitation period (e.g., the patient is on episodic regimen after completing the surgical/rehabilitation period, or the patient simply received no further prophylactic doses), then the end of the surgical/ rehabilitation period is:
  - Imputed as 23:59 on the last date among the dates for discharge from the hospital, post-operative visit 1, post-operative visit 2, and the end of rehabilitation.
  - If all of the dates mentioned above are missing, then the select the date of the end of surgery and impute 23:59 for the time. If the end date of the surgery is missing, then select the start date of the surgery and impute 23:59 for the time.
- If the overall end of study is declared while the patient is still in the surgical/ rehabilitation period then select the date of the end-of-study visit and impute 23:59 for the time if a time is not provided.

Two exceptions are noted:

- If 2 (or more) major surgeries are performed without an intervening discharge from the hospital, then the first surgical/rehabilitation period will end 1 minute before the start of the next surgery and the second surgical/rehabilitation will end as described above. The same will also apply among overlapping minor surgeries.
- If minor surgery is performed during postoperative care or rehabilitation then the surgical/rehabilitation period for the minor surgery will start and end on the day of the minor surgery, at 00:01 and 23:59, respectively, if times are not otherwise provided or

	Statistical Analysis Plan	Final v1.0
---	----------------------------------	-------------------

recorded as 00:00. The surgical/rehabilitation period for the major surgery will include the minor surgery (i.e., the surgical/rehabilitation period for the major surgery does not stop and restart around the minor surgery) and will end as otherwise defined.

The surgical/rehabilitation period will be determined in the same manner for both major and minor surgeries.

#### **5.4.4. ITI Period**

The ITI period is defined as the time from when a patient in the ITI sub-study begins this treatment regimen until they complete or withdraw from the study. The start of this period is the date and time of the first dose of the ITI regimen.

#### **5.4.5. Safety Period**

The overall safety period is defined as beginning at the first dose of study medication rFIXFc. For patients who are subsequently enrolled, the safety period ends on the date of the Final Safety Follow-up Visit (by telephone or in person), 14 (+7) days after the last dose of rFIXFc. For patients who fail screening, this period ends on the date that this is confirmed.

The safety period on a specific treatment regimen is as described in Section 5.3 except that the end of the patient's last treatment regimen is the end of their safety period.

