#### 5.1.1. Data Presentation

In general, presentations of background/demography and safety data will include an overall/total column and those for efficacy and health outcome data will not. Any exceptions to this are specified in the relevant section.

There is only 1 treatment arm in the study. However, unless otherwise stated, all analyses and background/demography tables will be presented for the following treatment groups, as defined in Section 3.1.2:

- Patients who were ever on an episodic regimen
- Patients who were ever on a prophylactic regimen
- Patients who were ever on an ITI regimen

For longitudinal data, the safety or efficacy periods included for these groups is the time spent on that regimen within that period. These periods are defined in Section 5.3 and 5.4.

Selected tables will also be presented by patients’ inhibitor development status, if there are at least 5 patients in the positive inhibitor subgroup (defined as in Section 5.2.4).

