### 5.3.1. Start Date and Time of the First Treatment Regimen

The start date and time of the first treatment regimen is defined as either:

- The date and time of the first rFIXFc dose for patients beginning on a prophylactic treatment regimen, as per the treatment assignment eCRF data.
- The date and time 120 hours after the date and time of the baseline PK dose for patients beginning on an episodic treatment regimen, as per the treatment assignment eCRF data.

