#### **5.4.2. Efficacy Period**

The efficacy period will be used for the evaluation of efficacy and health outcome endpoints. For a patient to have an evaluable efficacy period over the duration of study, he must have at least 1 day of treatment for an episodic regimen or at least 2 prophylactic injections for prophylactic regimens.

The start and end, and the total duration of the efficacy period for a given treatment regimen is the same as the start and end, and the total duration of that treatment regimen defined in Section 5.3.4 with the exceptions described in the following two subsections. The start of the efficacy period for each patient is the start of their first treatment regimen and the end is the end of their last.

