#### **6.6. Study Drug**

Study treatment is described in Section 3.1.2. Study drug administered will be listed by patient for the FAS. This will include the reason for administration (PK assessment, episodic (treatment of a bleeding episode), prophylaxis, ITI, surgery, other), date and time of administration, dose and dosing intervals, consumption and compliance. It will also include lot number and nominal potency of the lots used.

Except for PK doses, the unit body weight dose (IU/kg) for analysis of dosing will be calculated as the total IU (nominal dose) for each injection divided by the patient’s most recent weight in kg prior to the dose of study drug.

PK doses are all 50 IU/kg at the Baseline IR Visit and the ITI regimen IR assessments, and are calculated using the actual potency of the vial (between 80 to 125% of nominal strength) and using partial vials where necessary. Therefore PK doses in the analysis are similarly calculated using the exact number of complete and partial vials, the volume and actual potency of each vial and the patient’s most recent weight.

Both types of dose are calculated as follows:

$$\text{Dose (IU/kg)} = \frac{\left( \frac{\text{Total volume administered}}{\text{Volume of vial}} \right) \times \text{Actual/Nominal Potency of Vial}}{\text{Weight (kg)}}$$

PK doses are not used for the purpose of preventing or treating bleeding and therefore the total annualized rFIXFc consumption will exclude the IU/kg amount that is used for PK doses. However, data collected over the time in which the PK dose was administered will be included in the safety analyses.

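### For patients who start on episodic treatment, adverse events from the first study dose until 120 hours after the baseline recovery dose fall in no treatment-regimen column of the safety tables

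*SAP*

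**What the plan says.** SAP 5.4.5 gives two definitions. For the study as a whole, "The overall safety period is defined as beginning at the first dose of study medication rFIXFc". By regimen, "The safety period on a specific treatment regimen is as described in Section 5.3", with one change: the close of the last regimen moves to the close of the safety period. The end is adapted for safety; the start is left to Section 5.3.

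SAP 5.3.1 gives two start rules for the first regimen:

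- Episodic starters: "The date and time 120 hours after the date and time of the baseline PK dose for patients beginning on an episodic treatment regimen".
- Prophylaxis starters: "The date and time of the first rFIXFc dose for patients beginning on a prophylactic treatment regimen".

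SAP 5.1.1 says what goes into each regimen group: "For longitudinal data, the safety or efficacy periods included for these groups is the time spent on that regimen within that period". SAP 9.1 makes these groups the default layout for safety analyses, and SAP 5.1.1 adds an overall column to safety tables. SAP 6.6 removes PK doses from consumption but says that "data collected over the time in which the PK dose was administered will be included in the safety analyses".

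**The concern.** A 120-hour offset is understandable for bleeding rates, since it keeps the effect of the baseline dose out of the on-demand bleeding period. The SAP gives no reason for it in safety. Protocol 7.1 requires the first rFIXFc administration to be medically observed because of possible allergic reactions, so the days around first exposure matter for safety, which is the primary objective.

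As drafted, the same reaction to a first study dose is shown under prophylaxis for a child who starts on prophylaxis, and under no regimen for a child who starts episodically. The top-line and system-organ-class tables are specified by regimen (SAP 9.3.2 and 9.3.3). The table list in SAP 12 also titles the serious, severity, relationship and discontinuation tables by regimen. A reader of the episodic column would not know that its clock starts late.

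**Working it through.** No sample-size or test calculation applies, because the study is descriptive. The check is to put the date rules on one timeline and see where an event lands.

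**Inputs.** Hour 0 is the first dose of study rFIXFc.

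- Overall safety period: opens at hour 0 (SAP 5.4.5).
- Episodic regimen as first regimen: opens at the time of the PK dose + 120 h (SAP 5.3.1, carried into safety by 5.4.5).
- Prophylactic regimen as first regimen: opens at hour 0 (SAP 5.3.1).
- Switch from episodic to prophylaxis: the prophylactic regimen opens at the first prophylactic dose (SAP 5.3.3).
- Treatment-emergent status counts from the first injection (SAP 9.3.1), so events in the gap qualify.
- No PK period is defined to hold them (SAP 5.4.6).

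**The plan's own figure.** 120 h ÷ 24 = 5 days.

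**Formula.** Time in no regimen column = opening of the first applicable regimen period − hour 0.

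| Case | Opening of a regimen period | Time in no regimen column |
|---|---|---|
| Prophylaxis starter | hour 0 | 0 |
| Episodic starter, PK dose is the first dose | 0 + 120 = 120 h | 5 days |
| Episodic starter, bleed treated first, PK dose on day 14 (assumed example) | 14 × 24 + 120 = 456 h | 19 days |
| Episodic starter, first prophylactic dose at 72 h (assumed example) | 72 h, as prophylaxis | 3 days |

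In the second case, test events at 0.2, 24, 71, 100 and 119.9 h fall in the overall column only. An event at 120 h falls in episodic and overall. For the prophylaxis starter, all of these fall in prophylaxis and overall.

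The third case is possible because Protocol 7.3.1 lets the Baseline IR Visit be delayed until the child is not bleeding and a washout is feasible, with bleeds after eligibility treated with study drug. If no baseline PK dose is ever given, the episodic start is undefined.

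**Scale.** Expected participation is about 6 months to 3 years. Five days is 5 ÷ 182.6 = 2.74% of 6 months and 5 ÷ 1095.75 = 0.46% of 3 years. The number of episodic starters is not given. If 30% to 70% of about 30 children start that way (assumption: 9 to 21), one event confined to the gap would be 1/9 = 11.1% down to 1/21 = 4.8% of a column of that size. The column as defined would show none of it.

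**The case against.** The strongest reply is that nothing is lost. The overall safety period opens at the first study dose, safety tables carry an overall column, and all adverse events are listed. Allergic reactions of Grade 2 or higher must be reported as serious (Protocol 15.3.2) and lead to withdrawal (Protocol 11), so they also appear in the patient listings of SAP 9.3.7 and 9.3.8. SAP 9.3.5 to 9.3.7 describe overall summaries. All of this stands. A reader might infer that first-dose reactions are hidden from the safety analysis, and the documents do not support that.

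Three other inferences also go too far:

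- *SAP 6.6 is contradicted outright.* It promises inclusion in the safety analyses, not in a regimen column, and the overall column meets that literally. The tension is with the default by-regimen layout.
- *The columns fail to reconcile.* The groups are patients ever on a regimen, and one who switches appears in both (SAP 5.3). They were never meant to add up to the total.
- *The episodic regimen is made to look safer in a comparison.* No formal comparison is planned and the regimen is the Investigator's choice. The effect is on how a descriptive column reads.

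It can also be argued that a reaction to a recovery dose is not an event of on-demand treatment, so leaving it outside the episodic column is defensible. That is a fair view, but it would call for a stated rule and a labelled place for such events. It does not explain why a prophylaxis starter's events after the same baseline dose are counted under a regimen.

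**Conclusion.** The gap follows directly from the text, and no other section assigns this time to a regimen. It is a real inconsistency in the by-regimen safety tables, and a limited one. Its length is 5 days when the baseline dose is the first study dose. It should not be read as at least 5 days for every episodic starter, since it closes earlier if prophylaxis begins within 120 hours and runs longer if study-drug bleed treatment comes before the baseline dose.

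Nor should it be described as safety borrowing a rule that belongs to efficacy. Section 5.3 is a general regimen definition from which efficacy also takes its dates (SAP 5.4.2). The fault is that 5.4.5 adapted only one end of it.

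The primary inhibitor analysis counts any inhibitor after the initial rFIXFc administration in the whole Safety Analysis Set (SAP 9.4.3.2), so it does not change. The percentages shown for a single event rest on an assumed number of episodic starters and illustrate scale only.

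**What to change.** Add to SAP 5.4.5: 'For all patients the safety period on the first treatment regimen starts at the first dose of study rFIXFc; the 120-hour offset in Section 5.3.1 applies to the efficacy period only.'

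The word study matters. It matches the start of the overall safety period in 5.4.5. Commercial rFIXFc may precede enrolment, and events before consent are not recorded in the eCRF (Protocol 15.3.1), so a period opening at any rFIXFc dose could cover time with no data.

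The unassigned time for episodic starters then falls to zero, including where bleed treatment comes first or no baseline PK dose is given. The efficacy period and bleeding rates keep their present dates. SAP 6.6.1.2 also takes by-regimen dosing duration from 5.3.1, so the same edit should say which start that summary uses.

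The cost is one date derivation, with no new data. The small downside is that reactions to the recovery dose are attributed to the episodic column, which a table footnote can state.

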## 9. SAFETY ANALYSIS

### 9.1. General Safety Principles

Safety analyses will be based on the Safety Analysis Set and unless otherwise specified, presented by the treatment regimen groups described in Section 5.1.1.

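### By-regimen safety periods leave out the days after the first study dose for children who start on episodic treatment, but not for those who start on prophylaxis

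*SAP*

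**What the plan says.** SAP section 5.4.5 sets two kinds of safety period. For the whole study: "The overall safety period is defined as beginning at the first dose of study medication rFIXFc". For each regimen: "The safety period on a specific treatment regimen is as described in Section 5.3", with one exception, that the last regimen runs to the end of the patient's safety period. It makes no exception for the start.

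SAP section 5.3.1 gives two start rules for the first regimen:

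- Prophylaxis starters: "The date and time of the first rFIXFc dose for patients beginning on a prophylactic treatment regimen".
- Episodic starters: "The date and time 120 hours after the date and time of the baseline PK dose for patients beginning on an episodic treatment regimen".

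SAP section 5.1.1 forms the table columns from groups such as "Patients who were ever on an episodic regimen" and adds that "the safety or efficacy periods included for these groups is the time spent on that regimen within that period". It also gives safety tables a total column. Under section 9.1, safety results are by default "presented by the treatment regimen groups described in Section 5.1.1".

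On the PK dose itself, SAP section 6.6 says that "data collected over the time in which the PK dose was administered will be included in the safety analyses". SAP section 5.4.6 states that no PK period is defined, so no other period picks up the interval.

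**The concern.** The 120-hour offset makes sense for bleeding: the 50 IU/kg baseline dose protects the child for some days, and counting that time would flatter the episodic bleeding rate. The SAP gives no safety reason for it. SAP section 5.4.5 overrides the efficacy-style end of the last regimen, which would otherwise cut off follow-up, but does not do the same for the efficacy-style start.

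The days concerned follow the first study dose, which for many children will be their first exposure to any factor IX. Protocol section 7.1 requires the first administration to be under medical observation because of allergic reactions. A Grade 2 or greater allergic reaction must be reported as serious (Protocol section 15.3.2) and leads to withdrawal (Protocol section 11). If one followed an episodic starter's baseline dose, the episodic column of the top-line table in SAP section 9.3.2 would omit it from the rows for any event, related event, serious event and discontinuation. The same reaction in a prophylaxis starter would appear in the prophylactic column.

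**Working it through.** **Inputs**

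- Start of the overall safety period: first study dose, t = 0 (SAP 5.4.5).
- Start of an episodic first regimen: baseline PK dose + 120 h (SAP 5.3.1).
- Start of a prophylactic first regimen: first rFIXFc dose (SAP 5.3.1).
- Start of prophylaxis after episodic treatment: first prophylactic dose (SAP 5.3.3).
- Washout before the baseline incremental recovery (PK) dose: at least 72 h from any earlier rFIXFc (Protocol 4.2.1). Bleeds after eligibility are treated with study drug, and the baseline visit may wait (Protocol 7.3.1).

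**Formula**

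Gap = (earliest regimen safety start) − (first study dose). For an episodic starter this is (PK dose time − first dose time) + 120 h. The baseline PK dose is itself study drug, so it cannot precede the first study dose, and the bracket is never negative.

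**Results**

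| Case | Gap |
|---|---|
| Episodic starter, PK dose is first study dose | 0 + 120 = 120 h; 120/24 = 5.0 days |
| Episodic starter, bleed treated with study drug first | at least 72 + 120 = 192 h; 192/24 = 8.0 days |
| Episodic starter, PK dose first, first prophylactic dose at 96 h (illustrative) | 96 h; 4.0 days |
| Prophylaxis starter | 0 h |

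In the third case the SAP 5.3.3 start pre-empts the 120-hour mark. The derived episodic period would then start at 120 h and end one minute before 96 h, so its length is negative. If no baseline PK dose is given, the episodic start is undefined.

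The gap contains at least the first study exposure day. If a bleed is treated first it contains at least two, because the bleed dose and the PK dose are at least 72 h apart.

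**Share of participation**

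Five days is 5/182.6 = 2.7% of a 6-month participation and 5/1095.75 = 0.46% of a 3-year one. The amount of time is small; what matters is that it follows the first study dose.

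**Effect on a column**

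The documents do not say how many children start on episodic treatment. If the episodic column holds n children and one of them has his only event of a given kind in the gap, the percentage is too low by 100/n points. For assumed n:

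- n = 5: 20.0 points
- n = 10: 10.0 points
- n = 15: 6.7 points
- n = 20: 5.0 points

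This is the sensitivity to one child, not a forecast; no event rate is given.

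**A child withdrawn inside the gap**

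Say he stops on day 2. Under SAP 5.3.1 and 5.3.2 his episodic regimen could have a start later than its end. Under SAP 5.4.5 his safety period still runs to the follow-up contact, 14 (+7) days after the last dose. The SAP does not say whether he counts as ever having been on the episodic regimen. He may therefore be in the episodic denominator without his event, or in no regimen column at all.

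**The case against.** The strongest reply is that nothing is lost and no protocol rule is broken. Protocol section 16.5 plans safety summaries overall unless the SAP says otherwise. The total column runs from the first study dose, every adverse event is listed with its onset day, and SAP section 6.6 keeps PK-dose time in the safety analyses. All of this stands. A reader might infer that early reactions vanish from the report or that the inhibitor result is affected, and the documents support neither. The primary analysis in SAP section 9.4.3.2 counts every dosed patient and any inhibitor after the first administration. SAP section 6.6 does not, however, say which regimen column the interval belongs to.

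A second reply is that the split is a deliberate convention. The PK dose neither prevents nor treats a bleed, so a reaction to it is arguably not an event of on-demand treatment. SAP section 6.6.1.2 makes the same split for dosing duration: by regimen from section 5.3.1, overall from the first dose. As a convention it would be defensible if applied to both groups, but it is not. Section 5.3.1 starts a prophylaxis starter at the first rFIXFc dose, not the first prophylactic dose. The same baseline PK dose therefore counts under prophylaxis for one child and under no regimen for another. The parallel in section 6.6.1.2 does show that a fix confined to section 5.4.5 would put events and exposure on different clocks.

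Third, the study is descriptive, and the columns are overlapping groups of unequal duration that no analysis compares formally. This limits the consequence, but readers will still look at the columns side by side.

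**Conclusion.** The point holds as a fault of attribution by regimen. For an episodic starter, the time from the first study dose to 120 hours after the baseline PK dose falls in no regimen's safety period: 5 days in the simplest case, at least 8 if a bleed is treated with study drug first. For a prophylaxis starter the gap is zero. The episodic column therefore omits early reactions that the prophylactic column would show.

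Three stronger readings are tempting and go too far:

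- That every episodic starter loses the full 120 hours. Prophylaxis begun within 120 hours of the PK dose shortens the gap.
- That the affected child always stays in the episodic denominator. A child withdrawn in the gap may not enter it.
- That the lost days always follow first exposure. Protocol section 7.1 allows up to three earlier injections of commercial rFIXFc, and its observation rule covers those too.

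The conclusion rests on a literal reading of SAP sections 5.1.1, 5.3.1 and 5.4.5 together. Its practical size depends on the number of episodic starters and on early event rates, neither of which the documents give. It should be corrected, but it does not threaten the trial's main result.

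**What to change.** Amend the second paragraph of SAP section 5.4.5 so that the by-regimen safety period follows section 5.3 with two exceptions: the first regimen's safety period begins at the first dose of study rFIXFc, and the last regimen's ends when the overall safety period ends. Keep the 120-hour offset for the efficacy period only. This also gives a defined safety start to a child with no baseline PK dose.

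Use the same start for by-regimen exposure days, injections and dosing duration on the Safety Analysis Set (SAP sections 6.6.1.1 and 6.6.1.2), so that events and exposure match.

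If the sponsor would rather not attribute the baseline dose to episodic treatment, a separate column for the time before the first regimen would also close the gap. The exposure tables should then carry the same column.

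The cost is a short SAP edit and one derived start date, used in the adverse event and exposure programs. No new data are needed. The one drawback of the first option is that events after a non-therapeutic PK dose will count under episodic treatment, which a table footnote can state.
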